4.8.3. Subgroup analyses

To assess the effects of genetic factors and clinical severity of illness on treatment outcome, subgroup analyses for the primary endpoint, complete brain amyloid clearance, and mean changes in amyloid reduction will be conducted:

- Age - <65 , ≥ 65 .
- APOE4 Carrier Status – Carrier defined as E2/E4, E3/E4, or E4/E4 genotype; No-Carrier defined as all other genotypes
- Clinical staging at baseline – MCI (defined as $27 \leq \text{MMSE} \leq 30$) or mild AD (defined as $20 \leq \text{MMSE} \leq 26$)

The statistical models will be the same as those stated for the co-primary and key secondary objectives, with the addition of factors for the subgroup variable, the subgroup-by-treatment interaction, and the subgroup-by-visit interaction where appropriate.

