4.4. Co-Primary Endpoints Analysis

The primary objectives of this study are to test the hypothesis that participants treated with donanemab will have a significantly greater proportion of participants who reach amyloid plaque clearance compared to participants treated with aducanumab at the 6-month timepoint in both the ITT population and the intermediate tau subpopulation.

As the 6-month timepoint is the first scheduled opportunity to collect a post-baseline florbetapir F18 PET scan, the comparison of donanemab to aducanumab in complete brain amyloid clearance at 6 months will be performed using logistic regression. The logistic regression model will include fixed effect for treatment, ApoE $\epsilon 4$ genotype, baseline amyloid level, and baseline age. The test for this endpoint will be based on the contrast for the main effect of treatment from this logistic regression model. This analysis will be conducted on the full ITT population and the intermediate tau subpopulation. In case of quasi-complete separation of data points which may be possible due to small sample sizes, a Firth's penalized logistic regression model will be used to make inference on treatment efficacy.

Treatment effects from these logistic regression models will be summarized using estimated probabilities within each treatment group, along with odds ratios and a 100*(1- α)% confidence intervals, where α is the two-sided significance level for the primary endpoints.

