4.5.1.2. Main analytical approach

As there is only one post-baseline PET assessment within the first 6 months of the trial, mean change from baseline in amyloid plaque levels at Month 6 will be analyzed using an analysis of covariance model with the treatment group as fixed effect variable of interest, and APOE e4 genotype, baseline amyloid levels, and baseline age as the covariates. For the analysis of mean change from baseline at 12 and 18 months, a separate mixed model repeated measures (MMRM) analysis with data up to and including that specific time point will be used. This model will include the fixed effects of treatment, time, and treatment by time interaction, and APOE e4 genotype, and baseline amyloid level as covariates. Correlation among repeated measures on the same subject will be accounted for by enforcing an unstructured variance covariance matrix among the residuals. If the unstructured covariance structure matrix results in a lack of convergence, the following structures will be used in sequence until convergence is reached: heterogeneous Toeplitz covariance structure, heterogeneous autoregressive covariance structure,

heterogeneous compound symmetry covariance structure, and compound symmetry covariance structure. The Kenward-Roger approximation will be used to estimate the denominator degrees of freedom.

Time to amyloid plaque clearance between the two treatment groups will be analyzed and compared using a log-rank test for survival data. Kaplan-Meier estimates of percent of participants reaching amyloid plaque clearance and the p-value from the log-rank test will be used to determine the superiority of donanemab vs aducanumab in lowering time to plaque clearance.

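### The 12- and 18-month subgroup MMRMs omit subgroup-by-treatment-by-visit, so each assumes a subgroup difference in treatment effect that is constant over its visits

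*SAP*

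**What the plan says.** SAP 4.8.3 plans subgroup analyses of complete amyloid clearance and of mean change in amyloid, by age (under 65, 65 and over), APOE4 carrier status and clinical stage (MCI or mild AD by MMSE). Each factor has two levels. On the models it says: "The statistical models will be the same as those stated for the co-primary and key secondary objectives". To these models it adds a main effect for subgroup together with "the subgroup-by-treatment interaction, and the subgroup-by-visit interaction where appropriate".

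The models carried over are these:

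- **Clearance at 6 months (SAP 4.4).** The comparison of "complete brain amyloid clearance at 6 months will be performed using logistic regression", so it uses a single visit.
- **Mean change at 6 months (SAP 4.5.1.2).** "mean change from baseline in amyloid plaque levels at Month 6 will be analyzed using an analysis of covariance model", again on a single visit.
- **Mean change at 12 and 18 months (SAP 4.5.1.2).** For each, "a separate mixed model repeated measures (MMRM) analysis with data up to and including that specific time point will be used". The model has "fixed effects of treatment, time, and treatment by time interaction, and APOE e4 genotype, and baseline amyloid level as covariates", with an unstructured residual covariance and a fallback sequence.

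Neither the SAP nor the protocol mentions a subgroup-by-treatment-by-visit term. The qualifier at the end of the SAP 4.8.3 sentence applies to the subgroup-by-visit term and does not supply the missing one.

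**The concern.** The base MMRM lets the treatment effect differ by visit. The subgroup version lets subgroup means differ by visit, and lets the treatment effect differ by subgroup. It does not let the subgroup difference in treatment effect differ by visit. Within one model, the treatment effects in the two subgroups must run parallel over time.

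There is a design reason to doubt this. Under protocol 4.1, donanemab infusions stop after the Week 24 or Week 52 scan if plaque criteria are met, while aducanumab continues regardless. If one subgroup meets the criteria more often, its treatment contrast could evolve differently after Week 24 or Week 52. The planned model would then return a weighted average of the early and late subgroup differences in place of the difference at 12 or 18 months. A late divergence would usually be diluted, and the interaction test would lose power to detect it. What is at stake is the description of effect modification at 12 and 18 months.

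**Working it through.** **The plan's own figure.** The plan gives no power or precision for the subgroup analyses. Its only related figure is at least 98% power for each 6-month co-primary comparison. With 35.7% against 3.0% and two-sided 0.05, a two-proportion z-test gives 98.5% at 45 per arm and 99.2% at 50, so that figure reproduces. It has no bearing on this point.

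**Step 1: count the parameters.** Take two treatments, two subgroup levels and V visits, which makes 4V cell means. The model as written has V visit terms, V treatment-by-visit terms, V subgroup-by-visit terms and one subgroup-by-treatment term, so 3V + 1.

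- 6-month models, V = 1: 4 parameters for 4 cells. Nothing is constrained.
- 12-month MMRM, V = 2: 7 for 8 cells. One constraint.
- 18-month MMRM, V = 3: 10 for 12 cells. Two constraints.

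With the three-way term the counts become 4, 8 and 12, and every cell mean is free.

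**Step 2: what the constrained model estimates.** With complete data and residual covariance Σ, generalised least squares returns Σ w_v d_v (summed over visits). Here d_v is the true subgroup difference in treatment effect at visit v, and w = Σ⁻¹1 / (1'Σ⁻¹1). If all d_v are equal, the result equals that common value and there is no bias.

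**Step 3: illustration with equal SDs.** The documents give no SDs, correlations or subgroup effects, so these are assumptions: d = 0, -6, -12 centiloids at 6, 12 and 18 months, and correlations between 0.6 and 0.8.

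- *12-month MMRM.* With two equal-variance visits the weights are 0.5 and 0.5 at any correlation. Result: 0.5 × 0 + 0.5 × (-6) = **-3.0**, against a true -6.
- *18-month MMRM.* Let a, b, c be the correlations for 6 with 12, 6 with 18, and 12 with 18 months. The weights are proportional to (1-c)(1+c-a-b), (1-b)(1+b-a-c) and (1-a)(1+a-b-c).
  - a, b, c = 0.7, 0.6, 0.8: 0.10, 0.04, 0.09, which sum to 0.23, so the weights are 0.435, 0.174, 0.391. Result: -6 × 0.174 - 12 × 0.391 = **-5.7**, against a true -12.
  - 0.6, 0.7, 0.8: 0.10, 0.09, 0.04. Result: -6 × 0.391 - 12 × 0.174 = **-4.4**.
  - 0.8, 0.6, 0.7: 0.09, 0.04, 0.10. Result: -6 × 0.174 - 12 × 0.435 = **-6.3**.
  - Corners of the same range go further: 0.6, 0.8, 0.8 gives weights 0.5, 0.5, 0 and -3.0; 0.8, 0.8, 0.6 gives 0, 0.5, 0.5 and -9.0. None of these sets reaches -12.

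With two equal subgroups the error splits evenly. In the -5.7 case it is (12 - 5.74)/2 = 3.1 centiloids each. The affected subgroup's extra 18-month effect is shown as -8.9 instead of -12, and the other is given -3.1 instead of 0.

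**Step 4: dependence on nuisance parameters.** With assumed true differences of 0, 5 and 10, the 18-month model returns:

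| SDs at 6/12/18 months | Common correlation | Fitted difference |
|---|---|---|
| 25/25/25 | 0.5 | 5.0 |
| 20/25/30 | 0.5 | 1.9 |
| 20/25/30 | 0.7 | -0.1 |

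For subgroup shares of 30% to 70%, the bias in one subgroup's 18-month treatment effect runs from 1.5 to 7.1 centiloids in absolute value. With true differences 5, 5, 5 it is zero in every case.

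**Step 5: precision and power.** Protocol 9.5 expects about 90 evaluable per arm at 6 months. Assume two equal subgroups (45 per cell), complete data, SD 15 and the 0.7/0.6/0.8 correlations.

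- Visit-specific contrast: SE = √(4 × 15²/45) = √20 = 4.5.
- Constant difference: the variance is 20 divided by 1'R⁻¹1. The determinant of R is 1 + 0.672 - 0.49 - 0.36 - 0.64 = 0.182, and 1'R⁻¹1 = 0.23/0.182 = 1.264. SE = √(20/1.264) = 4.0.
- Power at 0.05 for the assumed 18-month pattern: Φ(12/4.47 - 1.96) = 77% with the visit-specific contrast, and Φ(5.74/3.98 - 1.96) = 30% with the constant difference.

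**The case against.** The case on the other side is substantial, and most of it limits the reach of the point.

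- **Results at 6 months.** A reader might infer that subgroup effects are distorted at all three time points, or that one value is imposed on all three. The documents do not support that. The 6-month results come from single-visit models in which subgroup-by-treatment is sufficient. The 12- and 18-month MMRMs are fitted separately, so their constants can differ, as -3.0 and -5.7 do above.
- **Stopping rule.** A reader might take donanemab-only stopping as proof that the assumption fails. By itself it makes the overall treatment effect change with time, and treatment-by-time already covers that. The three-way term matters only if the change differs by age, carrier status or stage. Nothing in either document shows this.
- **Reporting.** SAP 4.8.3 does not say which subgroup contrasts will be shown or at which visit, so it cannot be said that averages will be presented as visit-specific. But the base analyses are specific to 12 and 18 months, and the model offers no other estimate for those times.
- **Consequence.** The subgroup analyses lie outside the gated sequence in SAP 2.1, and SAP 4.1 allows additional exploratory analyses. With an SE of 4.5, the 3.1-centiloid bias in the illustration is below one SE of the visit-specific interaction, although the shortfall in the interaction itself (about 6.3) exceeds one.

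What remains is that the constancy assumption is built into the stated model, is not acknowledged or justified, and costs one term to remove.

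**Conclusion.** The point holds for the 12- and 18-month mean-change subgroup MMRMs only. As specified, each estimates a covariance-weighted average of the subgroup difference in treatment effect over its visits. That average equals the 12- or 18-month difference if the true difference is constant, and is in general biased if it changes. It would be too strong to say that the model cannot give correct visit-specific effects, because under constancy it does.

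The size is conditional on assumed inputs. With differences growing from 0 to -12 centiloids and equal SDs, the 12-month model recovers half of the true value. The 18-month model recovers roughly a third to a half for the correlation sets giving -4.4 to -6.3, and a quarter to three quarters at the corners of the 0.6 to 0.8 range. The two-subgroup setting matches the SAP; equal subgroup sizes and complete data are simplifications. No co-primary or gated key secondary conclusion changes. This is a minor improvement to the plan.

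**What to change.** Add to SAP 4.8.3 wording such as: for the 12- and 18-month mean-change subgroup MMRMs, the subgroup-by-treatment-by-visit interaction will also be included, and subgroup treatment effects and the interaction test will use the contrast at the visit in question. Apply the same rule to any repeated-measures subgroup model for clearance, if one is run. The 6-month logistic and ANCOVA subgroup models need no change.

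The cost is one extra parameter in the 12-month model and two in the 18-month model for each two-level subgroup factor, with somewhat wider subgroup intervals (interaction SE about 4.5 against 4.0 centiloids with 45 per cell and SD 15). No new data are needed, and the alpha allocation is unaffected.

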4.9. Interim Analyses

A planned interim analysis may be conducted for Study AACN as deemed by Lilly or its designee to assess for early efficacy of the two co-primary endpoints. No changes to the conduct of the study will result from executing an interim analysis, nor will the results of the interim impact the conduct of the study. Should an interim analysis be deemed necessary, it will be

performed by the independent data monitoring committee (IDMC), consisting of a minimum of 3 external members, including a physician with expertise in AD and a statistician who are independent experts not otherwise involved in the study, when approximately at least a sufficient number of participants (75-125) overall have had a chance to receive their 6-month amyloid PET scan. The analysis method for the primary efficacy endpoint described in Section 4.4 Co-Primary Endpoint Analysis will be used for the interim analysis.

Alpha Spending Approach for the Potential Interim Analysis Based on the group sequential design with the Pocock alpha spending approach, a 2-sided alpha of 0.03100566 will be allocated to the interim analysis for evaluating the efficacy of each of the two co-primary endpoints. If either of the null hypothesis for the two co-primary endpoints are not rejected at the interim analysis, both co-coprimary endpoints will be evaluated at the originally scheduled time point when all randomized participants have had a chance to complete their 6-month amyloid PET scan. This analysis would be performed at a 2-sided alpha level of 0.02774 to maintain strong control of an overall 2-sided Type I error rate of 5%.

The 2-sided alpha levels specified above were calculated assuming an information fraction of 0.50 or when data is available on 50% of participants. Depending on the actual information fraction at the time of the interim analysis, the alpha levels for the interim and final time points will be adjusted accordingly, but the Pocock spending function will still be utilized. The information fraction will be defined as the number of patients who were randomized prior to a specified date (patients included in the interim) divided by the total number of patients randomized.

If the interim analysis is deemed not necessary to be conducted by the sponsor, the primary efficacy analysis will be conducted when all participants have had a chance to receive their 6-month amyloid PET scan. This will be conducted at the two-sided significance level of 5%.

If an interim analysis is performed and both co-primary endpoints/null hypotheses are rejected, the 2-sided alpha available to test the four key secondary endpoints will be at least as much as 0.03100566 yet will be lower than 0.05. The alpha level will be determined using the approach outlined in Hung, Wang, and O'Neill (2007). If an interim analysis is performed and we fail to reject both co-primary endpoints, the co-primary endpoints will be re-tested (when all patients have their 6 month PET scan) and key secondary endpoints will be tested in a sequential/gated manner at a 2-sided alpha level of 0.02774 as determined by the Pocock alpha spending approach. The order of testing and the gating strategy for the key-secondary endpoints will be the same as detailed in Section 2.1.

4.10. Changes to Protocol-Planned Analyses

There are no changes to the protocol planned analyses at this time.

5. Sample Size Determination

This sample size will provide at least 98% power to demonstrate that donanemab is superior to aducanumab in achieving complete amyloid brain plaque clearance individually at 6 months in the overall population and the intermediate tau subpopulation. Power estimates were obtained using specific contrasts for the 6-month time point of treatment by time interaction effect within the framework of generalized linear mixed effect model assuming a logit link.

The assumptions for this power calculation are that 35.7%, 50.1%, and 54.6% of donanemab treated participants reach complete brain amyloid clearance at 6 months, 12 months, and 18 months, respectively. The corresponding complete brain amyloid clearance percentages for aducanumab treated participants are assumed to be 3.0%, 22.8%, and 27.8%, respectively. The simulation for the power calculation and sample size determination was carried out in SAS Enterprise Guide Version 7.15 and all sample size estimates were obtained assuming a 2-sided significance level of 0.05.

6. Supporting Documentation

6.1. Appendix 1: Protocol Deviations

Listings of patients with significant protocol violations will be provided for randomized participants. The following list of significant protocol violations will be determined from the clinical database and from the clinical/medical group:

- Informed consent violation detected as a missing date of informed consent.
- Did not have a florbetapir F18 PET scan at any of the visits at which the procedure scheduled to be collected.
- Incomplete infusions (any infusion at which less than 75%, approximately 105 mL, of the infusion solution is given).

The following list of significant protocol violations will be determined by clinical/medical group:

- Protocol violations of inclusion/exclusion criteria.
- Had a study dosing algorithm violation.

Other protocol deviations reported through the monitoring process will be reviewed by the study team and if judged to be significant, will be added to the final reported listing.

Summaries of significant protocol deviations will also be displayed by treatment group.

7. References

H. M. James Hung, Sue-Jane Wang & Robert O'Neill (2007) Statistical Considerations for Testing Multiple Endpoints in Group Sequential or Adaptive Clinical Trials, *Journal of Biopharmaceutical Statistics*, 17:6, 1201-1210

Leo Document ID = a3097bab-164d-418d-b7ff-b3ea9e7a2cd3

Approver: PPD

Approval Date & Time: 24-Sep-2021 17:08:06 GMT

Signature meaning: Approved
